8.2 Statistical methods

All statistical analysis will be performed according to the intention-to-treat principle. If ineligible patients are mistakenly included, they may be excluded (ref Ferguson et al BMJ 2002), apart from this, no other post-randomization exclusions will be made. The effect of treatment will be determined using 2x2 tables with assessment of the difference between patent vessels and prevalence of PTS, relative risks, and odds ratios with 95% confidence limits. The prevalence of clinically relevant bleeding, PTS, vein anomalies, thrombophilia, recurrent DVT will be determined using point estimates with 95% confidence intervals. A stratification analysis will be carried out using the Mantel-Haenzel method. Differences in baseline characteristics may be adjusted for using a multivariate logistic model. This may be done if there are substantial differences between the two groups, and if the variable(s) is probably or certainly associated with the outcome measure, e.g., age and previous VTE. Missing data on end-point variables will be scored as previous score or last/worst score carried forward.

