6 METHODS

6.1 DESIGN

Multi-center, open-label, randomized clinical study on the effect and safety of CDT therapy as compared with conventional therapy for the treatment of acute, first-time ilio-femoral DVT. The study will be a collaborative study of hospitals belonging to the Eastern and Southern Norway Health Authorities (Helse Øst and Sør).

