6.3 RANDOMIZATION

Patients will be randomized by sealed numbered envelopes using block randomization. Each envelope will contain information on treatment allocation. A new patient will be allocated the lowest numbered envelope. Treatment will be open-label, but stratified for extension of DVT, i.e., only femoral or iliofemoral DVT.

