6.4.2 Group I - Catheter-Directed Thrombolytic (CDT) therapy – procedures

- **Anticoagulant and fibrinolytic therapy**

- Discontinue oral anticoagulants - INR should be <1.5 before the procedure.
- In case of prior sc LMWH therapy treatment should be discontinued at least 8 h before the procedure, and in case of prior UFH treatment APTT (Cephotest®) should be adjusted to 40-60 sec during the procedure (see below).
- An iv bolus dose of UFH, 5000 U, should be given followed by continuous iv UFH¹ infusion at 15 U/kg/h. Adjust dose to keep APTT (Cephotest®) at 40-60 sec, first adjustment 6-12 h after start of treatment.
- During the thrombolytic treatment keep APTT (Cephotest®) at 40-60 sec.
- At the completion of thrombolytic treatment:
 - ✓ discontinue UFH
 - ✓ give sc LMWH after 1 h, (either dalteparin, Fragmin®, 200 U/kg bid, or enoxaparin, Klexane®, 1,5 mg/kg bid).
 - ✓ Oral warfarin (Marevan®) will be initiated according to local routines.
 - ✓ LMWH will be discontinued when INR has been in therapeutic range (2.0-3.0) for at least 24 hours, but should not be given for less than total 4-5 days.

- **Interventional procedures.** In an interventional radiology unit, an introducer will be inserted into an appropriate vein, preferentially the popliteal vein, guided by ultrasound to prevent puncture of the artery or laceration of the vein wall and to secure only a single puncture. If possible, the wire and catheter should be introduced above the proximal part of the thrombus (use fitting-sized perfusion catheters, e.g., 10, 20, 30, or 50 cm). A venography should then be performed to disclose the topography of the thrombus. CDT may be discontinued if introduction of the catheter through the occluded segment is not successful. Catheters should be properly fixed to the skin.

The perfusion catheter (and the perfusion wire) should cover the central to peripheral part of the thrombus. Rt-PA (Actilyse®), 20 mg diluted in 500 ml 0.9% NaCl, will be infused at 0.01 mg/kg/h. Maximal dose infused will be 20 mg/24 h. The rt-PA dosage may be split into two catheters using lower concentration, keeping flow the same.

¹ A suitable working solution should be made to contain UFH 40 U/ml in 0.9% NaCl, e.g., mix 20000 U of UFH in 500 ml 0.9% NaCl or 40000 U in 1000 ml 0.9% NaCl. The infusion rate (ml/h) then reflects total units of UFH per 24 hrs in thousands, e.g., 25 ml/h corresponds to 25000 U/24 h, 30 ml/h 30000 U/24 h, and so on.

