6.5 VISITS AND PROCEDURES DURING FOLLOW-UP

End-point assessment will be performed by a vascular surgeon with no previous contact or knowledge of patients' medical history or treatment allocation. At each visit the patients will explicitly be told not to reveal treatment allocation.

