6.5.2 Visit 2 (hospital stay)

- 6.5.2.1 Daily assessment of hemoglobin, platelets, fibrinogen, APTT, INR, and D-Dimer, and bilateral leg circumference.
- 6.5.2.2 Daily venography will be performed in patients allocated CDT.
- 6.5.2.4 Bleeding complications.

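### Section 8.2 lets ineligible patients be dropped after randomisation at discretion, on information that can differ by arm; the primary analysis should keep everyone randomised

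*Protocol*

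**What the plan says.** Section 8.2 opens with a general commitment: "All statistical analysis will be performed according to the intention-to-treat principle". The next sentence qualifies it: "If ineligible patients are mistakenly included, they may be excluded". It cites a methodological article in support, then closes the door on anything else: "apart from this, no other post-randomization exclusions will be made". So there is a single, openly declared exception.

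Four other parts of the protocol bear on how that exception would work:

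- **Open treatment.** Section 6.1 describes a "Multi-center, open-label, randomized clinical study", and Section 6.3 repeats that allocation is known: "Treatment will be open-label, but stratified for extension of DVT".
- **Blinding of outcomes only.** Section 6.5 states: "End-point assessment will be performed by a vascular surgeon with no previous contact or knowledge of patients' medical history or treatment allocation". Nothing comparable is stated for decisions about eligibility.
- **Imaging after randomisation.** Section 6.4.2, for the CDT arm, says after catheter placement: "A venography should then be performed to disclose the topography of the thrombus". Section 6.5.2 adds: "Daily venography will be performed in patients allocated CDT". No in-hospital venography is prescribed for controls.
- **Location as an eligibility criterion.** Section 5.1.3 requires thrombus in the upper thigh or iliac veins, verified by any one of four imaging methods.

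**The concern.** Intention-to-treat protects the comparison because the analysed groups are the randomised groups. An eligibility exclusion leaves that protection intact only if the same patients would have been excluded whichever arm they had been given. Section 8.2 does not secure this. Whether to exclude is left open, and the evidence of ineligibility may arise after allocation.

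In this trial the later evidence is unequal by design. A CDT patient whose entry ultrasound overstated the level of the thrombus can be found out at the first venogram; an identical control patient has no such examination and stays in. There is a lesser second route. Section 11.1 places CDT at four named centres while controls remain at their local hospital, so a new clinical team reviews patients in one arm only. The blinded assessment of end-points does not help, because the problem is who enters the analysis, not how the outcome is scored.

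At stake are both primary comparisons, patency at 6 months and PTS at 2 years. They are biased if exclusions differ by arm and those removed differ in prognosis from those kept.

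**Working it through.** **1. The plan's own figure.** Inputs from Section 8.1: PTS 25% versus 10%, significance level 5%, power 80%. Taking the test as two-sided (sidedness is not stated), with pooled variance and no continuity correction:

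n = [1.96 × √(2 × 0.175 × 0.825) + 0.842 × √(0.25 × 0.75 + 0.10 × 0.90)]² / 0.15² = (1.053 + 0.443)² / 0.0225 ≈ 100 per group.

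This reproduces the stated figure of approximately 100. Power with 100 per group is 80.2%.

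**2. Effect on power.** Five exclusions in the CDT arm only give 79.0%; five in each arm give 78.1%; ten in each arm give 75.9%. Loss of patients is not the main issue.

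**3. Effect on bias.** The protocol gives neither the number of exclusions nor the PTS risk of those excluded, so both are assumptions and are shown as a range. Suppose there is no true effect, with PTS 25% in both arms of 100. Remove k patients with PTS risk q from the CDT arm only.

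- Remaining CDT rate: r = (25 − kq) / (100 − k).
- Standard error under the null: s₀ = √[p̄(1 − p̄)(1/100 + 1/(100 − k))], where p̄ = (25 + 25 − kq) / (200 − k).
- Standard error of the difference: s₁ = √[0.25 × 0.75/100 + r(1 − r)/(100 − k)].
- Two-sided rejection rate, with d = 0.25 − r: Φ[(d − 1.96s₀)/s₁] + Φ[(−d − 1.96s₀)/s₁].

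Worked case, k = 5 and q = 1: r = 20/95 = 0.2105; d = 0.0395; s₀ = 0.0604; s₁ = 0.0602. The rejection rate is Φ(−1.31) + Φ(−2.62) = 0.095 + 0.004 ≈ 0.100.

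Each cell gives the remaining CDT PTS rate, then the type I error:

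| Removed from CDT | q = 25% | q = 50% | q = 75% | q = 100% |
|---|---|---|---|---|
| 3 | 25.0%, 5.0% | 24.2%, 5.2% | 23.5%, 5.7% | 22.7%, 6.7% |
| 5 | 25.0%, 5.0% | 23.7%, 5.5% | 22.4%, 7.1% | 21.1%, 10.0% |
| 10 | 25.0%, 5.0% | 22.2%, 7.3% | 19.4%, 14.9% | 16.7%, 28.8% |

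These are normal approximations. The first column shows that removing average-risk patients causes no bias. The last column is an extreme, in which every excluded patient would have had PTS.

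**4. Direction.** The table covers only removal of patients at average or higher risk. If the five removed had no PTS, the CDT rate would move the other way, to 25/95 = 26.3%, against CDT. The protocol gives some reason to expect this: Section 2 names extent of the initial thrombus among the risk factors for severe PTS found in some studies. A patient excluded because the thrombus lay too low could therefore be at lower risk than average.

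**The case against.** The case for leaving the text alone has several sound parts.

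- **The exception is narrow and declared.** It covers only patients entered by mistake, rests on a cited article, and is followed by a bar on all other exclusions. This stands. The article was not available, so whether it supplies the missing conditions cannot be judged; the protocol text itself does not state them.
- **Much of eligibility is fixed at entry in both arms.** Laboratory screening is done at Visit 1 for everyone, the daily blood tests in Section 6.5.2 are not restricted to one arm, and the symptom-onset limit comes from the history, not from a venogram. This stands too, and it narrows the unequal detection mainly to thrombus level.
- **Who adjudicates and when belongs in a statistical analysis plan.** Agreed, and those omissions are not the point. What the protocol does fix is a discretionary removal from the analysed population that is not tied to pre-randomisation information.

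Three stronger conclusions might be inferred, and the protocol does not support them.

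- *Failed procedures could be dropped.* No criterion in Section 5 concerns procedural failure. Section 6.4.2 treats an unsuccessful catheter passage as a reason to stop CDT, so Section 8.2 keeps those patients in.
- *The bias favours CDT.* The direction is not established, for the reason in step 4.
- *Two exclusions could make the trial significant.* A case can be built: 15/100 versus 25/100 gives p = 0.077 (Pearson chi-square, uncorrected), and dropping two CDT patients with PTS gives 13/98 and p = 0.036. But it starts from 15% rather than the planned rate below 10%, and requires both patients to have PTS. With one of the two affected (14/98), p = 0.058; with neither (15/98), p = 0.089. With continuity correction, 13/98 gives p = 0.055. At 10/100 versus 25/100, p is already 0.005. Section 8.2 also names no such test for the main comparison, only effect measures with 95% limits.

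**Conclusion.** The point holds as a weakness in a stated rule, not as evidence that the result will be biased. Section 8.2 declares intention-to-treat and then permits discretionary exclusion without limiting it to pre-randomisation facts, in an open-label trial whose design reveals thrombus level after randomisation in one arm only. Exclusions can therefore differ by arm, and both primary comparisons can be biased.

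Bias needs two conditions together: detection that differs by arm, and a different outcome risk in those removed. Its direction is uncertain and its size is probably small if few are excluded. For PTS with no true effect, five CDT-only removals at 50-100% risk raise the type I error to about 5.5-10%, three raise it to 5.2-6.7%, and removals at average risk leave it at 5.0%. The numbers removed and their risks are assumptions. The same reasoning applies to patency, for which no separate figure was calculated. The change should be made because the risk is avoidable at almost no cost.

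**What to change.** Amend Section 8.2 so that:

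1. The primary analysis includes all randomised patients in the arm to which they were allocated.
2. Any exclusion for ineligibility is a sensitivity analysis only. It is restricted to violations of Section 5 that can be proved from data recorded before randomisation, and is applied by the same rule to both arms, blind to allocation and outcome.
3. Findings from venography performed after randomisation are not grounds for exclusion.

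The change is best made before the patency analysis on the first 100 patients planned in Section 8.1, so that no eligibility decision is taken with results known. It takes a few lines of text, alters no trial procedure, and keeps the planned 100 per group with 80.2% power under the protocol's assumptions. The downside is that a few truly ineligible patients remain in the analysis and may dilute the effect slightly; the sensitivity analysis would give an indication of how much.

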9 ETHICAL CONSIDERATIONS

This study will recruit patients with proximal DVT. Even though the efficacy and safety of CDT for the treatment of acute proximal DVT remains to be established, some hospitals in many countries now offer CDT to selected patients with severe DVT, especially when the DVT extends into the caval vein. In the present study, non-trial CDT to selected patients with severe DVT will be left to the discretion of the responsible physician.

The study will be performed in accordance with the revised Helsinki Declaration and Good Clinical Practice (GCP). The study will only start after approval with the Regional Ethical Committee and the Norwegian Medical Agency. All patients will be given study specific identification codes and all data will be stored in a secured database on a secured server for research at the Ullevål University Hospital. This server as well as data management will be controlled by the Patient Protection Ombud at the Ullevål University Hospital. A non-linked database will provide information on the patients' contact information to allow follow-up. A biobank will be established at Ullevål University Hospital after approval.

10 MILESTONES

Q1-2006	First patient randomized
Q4-2007	Last patient randomized
Q2-2008	Six months follow-up of all patients for primary efficacy parameter patency
Q2-3-2008	Reporting of study design and primary efficacy parameter patency
Q4-2009	Two-years follow-up of all patients for primary efficacy parameter PTS
Q4-Q1-09-10	Reporting of primary efficacy parameter PTS
Q4-2012	Five years follow-up of last patient for patency and PTS.

11 TRIAL ORGANIZATION

11.1 GENERAL ORGANIZATION

The study is an investigator initiated study which will be run independently of the pharmaceutical industry. The study is financially supported by a grant from Eastern Norway Health Authority (doctoral fellow; Helse Øst grant no 2005-090).

The study will be a major collaborative effort among hospitals of the Eastern and Southern Norway Health Authorities (Helse Øst and Sør). All hospitals will be invited to participate in the study. Patients allocated to conventional treatment will be treated at the local hospital, whereas patients allocated CDT will be treated at Ullevål and Aker University Hospitals, the National Hospital and the Central Hospital in Østfold.

Appendix 2: VEINES-QoL and EQ-D5

Spørreskjema om helse

Opplysningene vil være til hjelp for å holde rede på hvordan du har det, og om hvordan du klarer å utføre dine vanlige aktiviteter.

Vis hvilke utsagn som passer best på **din helsetilstand i dag** ved å sette et kryss i en av rutene utenfor hver av gruppene nedenfor.

Gange

- Jeg har ingen problemer med å gå omkring.
- Jeg har litt problemer med å gå omkring.
- Jeg er sengeliggende.

Personlig stell

- Jeg har ingen problemer med personlig stell.
- Jeg har litt problemer med å vaske meg eller kle meg.
- Jeg er ute av stand til å vaske meg eller kle meg.

Vanlige gjøremål (*f.eks. arbeid, studier, husarbeid, familie- eller fritidsaktiviteter*).

- Jeg har ingen problemer med å utføre mine vanlige gjøremål
- Jeg har litt problemer med å utføre mine vanlige gjøremål.
- Jeg er ute av stand til å utføre mine vanlige gjøremål.

Smerte/ubehag

- Jeg har verken smerte eller ubehag.
- Jeg har moderat smerte eller ubehag.
- Jeg har sterk smerte eller ubehag.

Angst/depresjon

- Jeg er verken engstelig eller deprimert.
- Jeg er noe engstelig eller deprimert.
- Jeg er svært engstelig eller deprimert.

Besvar hvert spørsmål nedenfor ved å krysse av svaret som angitt. Hvis du er usikker på hva du skal svare, vennligst svar etter beste evne.

Disse spørsmålene er om din oppfatning av **beina dine**.

1. I løpet av de 4 siste ukene, hvor ofte har du hatt noen av disse plagene i beina?

(Sett ett kryss på hver linje)	Daglig	Flere ganger i uka	Omtrent én gang i uka	Sjeldnere enn én gang i uka	Aldri
1. Tunge bein	 ₁	 ₂	 ₃	 ₄	 ₅
2. Vondt i beina	 ₁	 ₂	 ₃	 ₄	 ₅
3. Hevelse	 ₁	 ₂	 ₃	 ₄	 ₅
4. Kramper om natta	 ₁	 ₂	 ₃	 ₄	 ₅
5. Varme eller brennende følelse	 ₁	 ₂	 ₃	 ₄	 ₅
6. Urolige bein	 ₁	 ₂	 ₃	 ₄	 ₅
7. Banking	 ₁	 ₂	 ₃	 ₄	 ₅
8. Kløe	 ₁	 ₂	 ₃	 ₄	 ₅
9. Prikking	 ₁	 ₂	 ₃	 ₄	 ₅

2. Når på dagen er **plagene i beina** mest uttalte? (Sett ett kryss)

- | | |
|---|--|
|  ₁ Når jeg våkner |  ₄ Om natta |
|  ₂ Midt på dagen |  ₅ Når som helst i løpet av dagen |
|  ₃ På slutten av dagen |  ₆ Aldri |

3. Sammenlignet med for ett år siden, hvordan vil du vurdere dine **plager i beina nå**? (Sett ett kryss)

- | | |
|---|---|
|  ₁ Mye bedre nå enn for ett år siden |  ₄ Noe verre nå enn for ett år siden |
|  ₂ Noe bedre nå enn for ett år siden |  ₅ Mye verre nå enn for ett år siden |
|  ₃ Omtrent det samme nå som for ett år siden |  ₆ Jeg hadde ingen plager i beina i fjor |

4. Følgende spørsmål gjelder daglige aktiviteter. Setter **plagene i beina** begrensninger for dine daglige aktiviteter? Hvis « ja », i hvilken grad?

(Sett ett kryss på hver linje)	Jeg jobber ikke	JA, begrenser meg mye	JA, begrenser meg litt	NEI, begrenser meg ikke
a. Daglige aktiviteter på jobb.	 0	 1	 2	 3
b. Daglige aktiviteter hjemme (husarbeid, småjobber, hagearbeid, o.l.)		 1	 2	 3
c. Fritidsaktiviteter hvor du må stå lenge (selskap, ta buss, handle o.l.)		 1	 2	 3
d. Fritidsaktiviteter hvor du må sitte lenge (kino, teater, på reise o.l.)		 1	 2	 3

5. 3. I løpet av de 4 siste ukene , har du hatt noen av disse problemene i jobb eller i daglige aktiviteter på grunn av plagene i beina ?		
(Sett ett kryss på hver linje)	JA	NEI
a. Redusert arbeidstid eller tid til andre aktiviteter	 1	 2
b. Gjennomført mindre enn du skulle ønsket	 1	 2
c. Blitt begrenset i type jobb eller aktiviteter	 1	 2
d. Hatt vanskeligheter med å utføre jobben eller andre aktiviteter (f eks det krevde større anstrengelse)	 1	 2

6. I løpet av de 4 siste ukene , i hvilken grad har plagene i beina kommet i veien for samvær med familie, venner, naboer eller grupper? (Sett ett kryss)	
 1 Ikke i det hele tatt	 4 Ganske stor
 2 Lett	 5 Svær
 3 Moderat	

7. Hvor mye smerter har du hatt i beina i løpet av de 4 siste ukene ? (sett ett kryss)	
 1 Ingen	 4 Moderat
 2 Svært lite	 5 Mye
 3 Lite	 6 Svært mye

8. Disse spørsmålene er om hvordan du føler deg, og om hvordan du har hatt det de siste 4 ukene som følge av plagene i beina . For hvert spørsmål, kryss av for det svaret som passer best med hvordan du har følt deg. Hvor mye i løpet av de 4 siste ukene -						
(Sett ett kryss på hver linje)	Hele tiden	Det meste av tiden	Ganske ofte	Av og til	Sjelden	Aldri

a.	har du vært bekymret for hvordan beina dine ser ut?	 1	 2	 3	 4	 5	 6
b.	har du følt deg irritabel	 1	 2	 3	 4	 5	 6
c.	har du følt at du har vært til byrde for familie eller venner?	 1	 2	 3	 4	 5	 6
d.	har du vært bekymret for å skumpe bort ting?	 1	 2	 3	 4	 5	 6
e.	har dine beins utseende påvirket ditt klesvalg ?	 1	 2	 3	 4	 5	 6

Vennligst oppgi dato for utfyllingen: ____/____/____ (dag/måned/år)
